8.2. Other Efficacy Endpoints and Analyses

8.2.1. Global Response by Principal Investigator

Global Response as determined by Principal Investigator will be analyzed for the ITT Population as for the Global Response by the DRC, see Section 8.1.

8.2.2. Overall Survival

Overall survival is defined as the time from randomization to time of death up to Day 84.

Subjects with death will be censored at Day 84, date of withdrawal or date of last follow up whichever comes earliest.

Overall survival will be expressed in days and calculated using the formula:

$$\text{Overall Survival} = \text{Date of Death/Censoring} - \text{Date of Randomization.}$$

The number and percentage of subjects with events and censored will be summarized.

The Kaplan-Meier method will be used to estimate the distribution of overall survival for each treatment group. The 25th percentile, median and 75th percentile overall survival and their 95% CIs will be presented. In addition, the overall survival (%) at Day 42 and Day 84 and their 95% CIs will also be presented.

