The largest randomized controlled study evaluating antifungal combination therapy for patients with IPA was reported by Marr K et al. in 2015.⁷ This study assessed the safety and efficacy of voriconazole and anidulafungin compared with voriconazole monotherapy for the treatment of IPA. The study included 454 patients with hematological malignancies or hematopoietic stem cell transplantation and suspected or documented IPA and the primary analysis was done in 277 patients with documented IPA. Although the study failed to demonstrate statistically significant improvement in all-cause mortality with the combination therapy when compared with monotherapy, there was a clear trend towards improved survival in the group receiving combination therapy. Overall mortality rates at 6 weeks were 19.3% (26 of 135) for combination therapy and 27.5% (39 of 142) for monotherapy (difference, - 8.2 percentage points [95% CI, - 19.0 to 1.5]; P = 0.087).

Most patients (218 of 277 [78.7%]) had a diagnosis of IPA established by radiographic findings and mycological evidence in the form of galactomannan positivity. In a post hoc analysis of this dominant subgroup, 6-week mortality was lower in combination therapy than in monotherapy (15.7% [17 of 108] vs. 27.3% [30 of 110]; difference, -11.5 percentage points [CI, -22.7 to -0.4]; P= 0.037). A limitation of this study was that anidulafungin is only available intravenously (IV), thus limiting its use for long-term administration as often needed in IPA patients, resulting in a median duration of the combination therapy of 14 days.

SCY-078 antifungal activity

The spectrum and potency of activity of SCY-078 has been evaluated by numerous independent laboratories against an extensive panel of clinically relevant yeast and mold isolates using the Clinical and Laboratory Standards Institute (CLSI) and European Committee on Antimicrobial Susceptibility Testing (EUCAST) methods. Overall, the epidemiological studies have demonstrated that SCY-078 has potent, broad-spectrum activity against the majority of the clinical isolates tested. These studies have laid the foundation in support of the use of SCY-078 for the treatment of invasive fungal infections.

In vitro activity against Candida spp.

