15.23 Survival

Survival will be determined on Day 42 and Day 84 (42 and 84 days after Baseline [Treatment Day 1] [first dose of study drug] for randomized subjects and 42 and 84 days after the ICF is signed for screen failures). This can be an in-person visit or a phone contact, and will document subject status (alive or deceased). If subject is deceased, the date of death and the investigator's assessed relationship to the fungal infection will also be recorded. If autopsy is conducted, key findings should be collected in the eCRF.

See Section 19.7 for a detailed description of efficacy outcomes.

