4.2. Secondary Endpoints

- Global Response as measured by:
 - Percentage of subjects with Complete Response or Partial Response at EoT (key secondary endpoint), Day 42 and Day 84, as determined by the DRC
 - Percentage of subjects with Complete Response or Partial Response at EoT, Day 42 and Day 84, as determined by the Principal Investigator
- Overall survival, defined as the time from randomization to time of death up to Day 84
- Percentage of subjects who died (any cause) at Days 42 and 84
- Absolute reduction and percent change in serum GMI from Baseline to Weeks 1, 2, 4 and 6
- Percentage of subjects with the following changes in serum GMI from Baseline:
 - Fifty percent reduction or greater at Weeks 1, 2, 4 and 6
 - Twenty-five percent reduction or greater at Weeks 1, 2, 4 and 6
 - Any percent reduction at Weeks 1, 2, 4 and 6
 - Reduction equal to or greater than 0.25 at Weeks 1, 2, 4 and 6
 - Reduction to <0.5 at Weeks 1, 2, 4 and 6
- Time to achieve the following changes in serum GMI from Baseline:
 - Fifty percent reduction
 - Twenty-five percent reduction
 - Any percent reduction
 - Reduction equal to or greater than 0.25
 - Reduction to <0.5 in 2 consecutive samples
- Percentage of subjects with:
 - Clinical Response at EoT, Day 42 and Day 84, as determined by the DRC
 - Mycological Response at EoT, Day 42 and Day 84, as determined by the DRC
 - Radiological Response at EoT, Day 42 and Day 84, as determined by the DRC

- Percentage of subjects with:
 - Clinical Response at EoT, Day 42 and Day 84, as determined by the Principal Investigator
 - Mycological Response at EoT, Day 42 and Day 84, as determined by the Principal Investigator
 - Radiological Response at EoT, Day 42 and Day 84, as determined by the Principal Investigator
- Ibrexafungerp and voriconazole plasma concentrations population PK analysis.

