8.2.3. All-Cause Mortality

All-cause mortality is defined as all deaths following the first dose of study drug, regardless of attribution. The total number of deaths by Day 42 and Day 84 and relationship to the fungal infection will be summarized. The difference in mortality rates between treatments will be presented along with a 95% CI calculated using the method of Clopper-Pearson.

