8.2.6. Time to Achieve Target Changes in GMI from Baseline

The following targets will be considered:

- Fifty percent reduction
- Twenty-five percent reduction
- Any percent reduction
- Reduction equal to or greater than 0.25
- Reduction to < 0.5 in 2 consecutive samples

Time to achieve a target change in serum GMI from baseline will be expressed in days and calculated using the formula:

$$\text{Time to Achieve} = \text{Date of Achievement/Censoring} - \text{Date of Randomization.}$$

Subjects not achieving the target by Day 84 will be censored at Day 84 Or date of death, or date of withdraw, or date of last GMI assessment whichever comes earliest.

The number and percentage of subjects with events and censored will be summarized.

The Kaplan-Meier method will be used to estimate the distribution of time to achieve target for each treatment group. The 25th percentile, median and 75th percentile and their 95% CIs will be presented.

8.2.7. Clinical Response, Mycological Response and Radiological Response at EoT, Day 42 and Day 84 as determined by the DRC

Clinical Response, Mycological Response and Radiological Response at EoT, Day 42 and Day 84 as determined by the DRC will be analyzed for the ITT Population as for the Global Response by the DRC, see Section 8.1.

8.2.8. Clinical Response, Mycological Response and Radiological Response at EoT, Day 42 and Day 84 as determined by Principal Investigator

Clinical Response, Mycological Response and Radiological Response at EoT, Day 42 and Day 84 as determined by Principal Investigator will be analyzed for the ITT Population as for the Global Response by the DRC, see Section 8.1.

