10.7. Physical Examination

A general physical examination is done at Screening, Day 1, Day 14, Day 28, Day 42, Day 56, Day 70, Day 84, EoT and at Follow-Up.

Physical examination results will be summarized, by treatment, for the Safety Population.

11. Interim Analyses

The protocol planned for the performance of an interim analysis. However, there is no interim analysis since the study was stopped after enrolment of 22 subjects, due to patient recruitment challenges..

12. Changes from Analysis Planned in Protocol

There are currently no deviations from the analyses planned in the protocol. Enrollment into the study was stopped after 22 subjects were randomized because of the subject recruitment challenges and feasibility to enrol the planned sample size of 60 subjects.

13. Programming Considerations

All tables, figures, listings (TFLs), and statistical analyses will be generated using SAS for Windows, Release 9.4 or higher (SAS Institute Inc., Cary, NC, USA). Computer-generated table, listing and figure output will adhere to the following specifications.

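### SAP 8.2.2 writes its only overall-survival censoring rule for subjects who died, almost certainly a slip for subjects who did not (minor)

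*SAP*

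**What the plan says.** SAP 4.2 lists the endpoint among the secondary endpoints: "Overall survival, defined as the time from randomization to time of death up to Day 84". SAP 8.2.2 repeats that definition and then gives its censoring rule: "Subjects with death will be censored at Day 84, date of withdrawal or date of last follow up whichever comes earliest". The formula that follows subtracts the randomization date from an end date that is either the date of death or the date of censoring. The section continues: "The number and percentage of subjects with events and censored will be summarized". It plans Kaplan-Meier quartiles and survival percentages at Days 42 and 84, all with 95% confidence intervals.

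SAP 8.2.3 counts the same deaths directly: "The total number of deaths by Day 42 and Day 84 and relationship to the fungal infection will be summarized".

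Neither document has another censoring rule for this endpoint. Protocol 10.2 gives the definition only, and protocol 19.7.2 adds a Kaplan-Meier plot. SAP 6.3 says that data from withdrawn subjects are used where possible and assigns a failure outcome when the end-of-treatment assessment is missing. Neither statement supplies a censoring date.

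**The concern.** The sentence is addressed to the wrong group. In a time-to-death analysis the deaths are the events, and censoring is for everyone else. As worded, the rule censors the deaths and says nothing about subjects who are alive, withdrawn or lost.

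This is the operative instruction for the survival dataset. A programmer would have to code a rule that defeats the endpoint or depart from the SAP without a documented basis. If the literal rule were coded, the Kaplan-Meier output would not reconcile with the deaths tabulated under SAP 8.2.3 in the same report.

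**Working it through.** The plan states no survival figure, event target or power for this endpoint, so there is nothing to reproduce. The check is a comparison of the text, followed by an illustration of size.

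**1. The rule against the rest of SAP 8.2.2**

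| Element of the section | What it requires | Under the literal rule |
|---|---|---|
| Definition | Death is the event | Death is censored |
| Formula | End date is death or, failing that, censoring | The death date is never used as an event date; survivors have neither date |
| Count of events and censored | Two separate groups | No events; survivors in neither group |
| Dates listed (Day 84, withdrawal, last follow-up) | Dates on which follow-up without death ends | Applied to subjects who died |

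**2. The rule against the parallel sections.** SAP 8.2.6 begins its rule "Subjects not achieving the target by Day 84 will be censored at Day 84 Or date of death, or date of withdraw". SAP 8.2.13 likewise addresses subjects who did not reach the 10-point improvement. Both censor subjects *without* the event; only 8.2.2 is worded the other way round.

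**3. How many subjects the wording touches.** Inputs:
- Number randomized: 22 (SAP section 12: "Enrollment into the study was stopped after 22 subjects were randomized because of the subject recruitment challenges"), with 11 per group (SAP 3.4).
- Assumed 6-week mortality, m: from the combination trial described in protocol 8.1, "Overall mortality rates at 6 weeks were 19.3% (26 of 135) for combination therapy and 27.5% (39 of 142) for monotherapy". This is borrowed for illustration. That trial enrolled patients with hematological malignancy or stem cell transplantation, a narrower population than this one.

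Expected deaths by Day 42 are 22 × m:
- m = 0.193: 22 × 0.193 = 4.2 deaths, leaving 17.8 subjects with no rule.
- m = 0.275: 22 × 0.275 = 6.1 deaths, leaving 16.0 subjects with no rule.

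The probability of no death at all among 22 is (1 − m)^22:
- 0.807^22 = 0.0089, or 0.9%.
- 0.725^22 = 0.0008, or 0.1%.

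At these rates some death by Day 42 is nearly certain, so a mismatch with SAP 8.2.3 would show if the literal rule were coded.

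**4. What the estimate would be for one arm of 11.** Assume all deaths fall before Day 42 and everyone else is followed to Day 84. With subjects *without* death censored, the product-limit estimate at Days 42 and 84 is:
- 2 deaths (11 × 0.193 = 2.1): (10/11) × (9/10) = 9/11 = 81.8%, standard error √(0.818 × 0.182 / 11) = 11.6 points; 2 events, 9 censored.
- 3 deaths (11 × 0.275 = 3.0): (10/11) × (9/10) × (8/9) = 8/11 = 72.7%, standard error √(0.727 × 0.273 / 11) = 13.4 points; 3 events, 8 censored.

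Each value equals 1 minus the crude mortality, as it should with complete follow-up. Under the literal rule the same arms have 0 events, and 9 or 8 of the 11 subjects have no end date. If survivors are then censored at Day 84, which the SAP does not say, the curve stays at 100% and no quartile can be estimated.

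**The case against.** The strongest reply is that the slip corrects itself. The definition, the formula, the event count and the choice of dates all point to *without*, and two neighbouring sections show the intended pattern. A competent programmer would notice. The lack of a rule for survivors is not a second defect, because the same missing syllable produces both effects. The endpoint is descriptive, in an exploratory study with no formal sample size calculation (protocol 19.1, SAP 3.6), and mortality at Days 42 and 84 is reported separately. All of this stands, and it sets the severity. It does not make the sentence right: it remains the only censoring rule for a named secondary endpoint, and it says the opposite of what the analysis needs.

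It could also be said that the sentence works for a death after Day 84, which would properly be censored at Day 84. That is true, but the sentence is not limited to that case and would still leave survivors uncovered.

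A reader might infer that the trial will report 100% survival. The documents do not support that. It would take someone coding a reading that the section itself rules out, and adding a survivor rule that the text lacks.

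A reader might also infer that 8.2.6 and 8.2.13 are wrong because they list death among the censoring dates. Those rules are explicit and programmable and feed descriptive per-arm percentiles. Whether to treat death as a competing event there is a choice of method, not an error in the plan.

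**Conclusion.** The rule is wrong as written, and the severity is minor. One word, almost certainly *with* for *without*, turns deaths into censored observations and leaves living subjects with no censoring date. This contradicts the section's own definition, formula and event count and conflicts with the deaths counted in SAP 8.2.3. That conclusion rests on the text alone.

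The figure of roughly 4 to 6 affected deaths among 22 rests on borrowed 6-week mortality. It shows how visible a literal coding would be; it does not predict harm.

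The effect is confined to the overall-survival output of 8.2.2. The primary safety endpoint, Global Response and all-cause mortality under 8.2.3 do not use this rule, and no error rate, power or sample size depends on it. A reader who took the slip as grounds to doubt the trial's mortality results in general would be going beyond the documents.

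**What to change.** Replace the censoring sentence in SAP 8.2.2 with a rule to this effect:

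> A death on or before Day 84 is an event, dated on the day of death. A subject with no death on or before Day 84 is censored at the earliest of Day 84, the date of withdrawal and the date of last follow-up.

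This keeps the SAP's three dates, covers survivors, and also handles a death after Day 84. SAP 8.2.6 and 8.2.13 need no change for this point.

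The cost is a short rewording. No new data are needed: protocol 15.23 already collects vital status at Days 42 and 84 ("This can be an in-person visit or a phone contact, and will document subject status (alive or deceased") and the date of any death. After the change, the event counts by Days 42 and 84 should be reconciled with the deaths tabulated under SAP 8.2.3.

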8.2.3. All-Cause Mortality

All-cause mortality is defined as all deaths following the first dose of study drug, regardless of attribution. The total number of deaths by Day 42 and Day 84 and relationship to the fungal infection will be summarized. The difference in mortality rates between treatments will be presented along with a 95% CI calculated using the method of Clopper-Pearson.

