5.2. Intent-to-Treat (ITT) Population

The ITT Population will include all randomized subject who receive at least one dose of randomized study medication. This population will be the primary population for the analysis of efficacy data. Analysis will be according to randomized treatment.

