6.3. Missing Data

Data from subjects who withdraw will be included, where possible, in all summaries and analyses.

For the efficacy analyses, subjects who do not have an EoT assessment will be assigned an indeterminate outcome, so will be classed as treatment failures for the corresponding efficacy analyses. For subjects who withdraw from the study early, every effort will be made to collect EoT visit information at the point of withdrawal.

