13.2.5.2. Table Conventions

- Units will be included where available
- If the categories of a parameter are ordered, then all categories between the maximum and minimum category are presented in the table, even if n=0 for all treatment groups in a given category that is between the minimum and maximum level for that parameter. For example, the frequency distribution for symptom severity would appear as:

Severity Rating	N
severe	0
moderate	8
mild	3

Where percentages are presented in these tables, zero percentages will not be presented and so counts of 0 will be presented as 0 and not as 0 (0%).

- If the categories are not ordered (e.g., Medical History, Reasons for Discontinuation from the Study, etc.), then only those categories for which there is at least 1 subject represented in 1 or more groups are included.
- An Unknown or Missing category are added to each parameter for which information is not available for 1 or more subjects.
- Unless otherwise specified, the estimated mean and median for a set of values are printed out to 1 more significant digit than the original values, and standard deviations are printed out to 2 more significant digits than the original values. The minimum and maximum should report the same significant digits as the original values. For example, for systolic blood pressure:

n	XX
Mean	XXX.X
Std Dev	X.XX
Median	XXX.X
Min	XXX
Max	XXX

- P-values are output in the format: “0.xxx”, where xxx is the value rounded to 3 decimal places. Every p-value less than 0.001 will be presented as <0.001. If the p-value are less than 0.0001, then present as <0.0001. If the p-value is returned as >0.999, then present as >0.999.
- Percentage values are printed to one decimal place, in parentheses with no spaces, one space after the count (e.g., 7 (12.8%), 13 (5.4%)). Values that round down to <1% will be displayed as '<1'. Unless otherwise noted, for all percentages, the number of subjects in the analysis set for the treatment group who have an observation will be the denominator. Percentages after zero counts should not be displayed and percentages equating to 100% are presented as 100%, without decimal places.
- Tabular display of data for medical history, prior/concomitant medications, and all tabular displays of adverse event data are presented by the body system, treatment class, or SOC with the highest occurrence in the ibrexafungerp + Voriconazole treatment group in decreasing order, assuming all terms are coded. Within

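### The Day 42 and Day 84 mortality difference is a crude rate with no rule for unknown vital status, and it need not match the Kaplan-Meier survival reported beside it

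*SAP*

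**What the plan says.** The endpoint in SAP 4.2 is "Percentage of subjects who died (any cause) at Days 42 and 84". SAP 8.2.3 implements it with death counts ("The total number of deaths by Day 42 and Day 84 and relationship to the fungal infection will be summarized") and then states: "The difference in mortality rates between treatments will be presented along with a 95% CI calculated using the method of Clopper-Pearson". It names neither a population nor a denominator. SAP 5.2 supplies the population, since it says of the ITT set: "This population will be the primary population for the analysis of efficacy data".

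Three other places bear on subjects whose status is not known:

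- **SAP 6.3, general sentence:** "Data from subjects who withdraw will be included, where possible, in all summaries and analyses". It does not say what outcome they are given.
- **SAP 6.3, imputation rule:** "subjects who do not have an EoT assessment will be assigned an indeterminate outcome, so will be classed as treatment failures". This concerns the EoT assessment only. SAP 8.1 has a rule for missing Day 42 and Day 84 data, but for response; 8.2.7 and 8.2.8 adopt it by cross-reference and 8.2.3 does not.
- **SAP 13.2.5.2, default for percentages unless otherwise noted:** "the number of subjects in the analysis set for the treatment group who have an observation will be the denominator".

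SAP 8.2.2 estimates survival by Kaplan-Meier, censoring at Day 84, withdrawal or last follow-up, and "the overall survival (%) at Day 42 and Day 84 and their 95% CIs will also be presented". Its clock starts at randomization. SAP 8.2.3 counts deaths after the first dose, and Protocol 15.23 counts Days 42 and 84 from the first dose. Nothing links the two sections.

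**The concern.** A subject lost on Day 10 has no recorded death and no recorded status at Day 42. Two readings of 8.2.3 are open. Under 13.2.5.2 the subject leaves the denominator, while a subject who died on Day 9 stays in both numerator and denominator; this tends to overstate mortality. With the ITT count as denominator, the lost subject is in effect a survivor to Day 84; this tends to understate it. If losses differ between arms, the choice moves the difference.

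Protocol 19.7.1 lists mortality among the three main efficacy measures, and Protocol 19.1 gives preliminary effect sizes as the main goal of the study. An effect size that depends on an unstated convention serves that goal poorly. The report could also show, for one arm and one day, a mortality percentage and a Kaplan-Meier survival percentage that do not add to 100, with no explanation.

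**Working it through.** The plan states no mortality rate, sample size or power for this endpoint, so there is no figure of its own to reproduce.

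**Inputs.** About 11 subjects per arm (SAP 3.4). For scale, the cited combination trial in Protocol 8.1 had 6-week mortality of 26/135 = 19.3% and 39/142 = 27.5%, which is roughly 2/11 and 3/11. The number with unknown status is not given; I assume 0 to 3 per arm. All event days below are also assumed.

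**One arm of 11, deaths on Days 12, 20 and 35.** Every assumed loss falls before Day 42, so the Day 42 and Day 84 results are the same.

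- All-ITT denominator: 3/11 = 27.3% whatever the losses.
- Unknowns dropped: 3/(11 − u), where u is the number lost.
- Kaplan-Meier: 1 − product of (1 − 1/number at risk) over the death days.
  - Losses on Days 8 and 15: 1 − (9/10 × 7/8 × 6/7) = 1 − 0.675 = 32.5%.
  - Losses on Days 8, 15 and 18: 1 − (9/10 × 6/7 × 5/6) = 1 − 0.643 = 35.7%.
  - Losses on Days 36 and 38: 1 − (10/11 × 9/10 × 8/9) = 27.3%.

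| Losses on days | All ITT | Dropped | Kaplan-Meier | Unknown as dead |
|---|---|---|---|---|
| none | 27.3% | 27.3% | 27.3% | 27.3% |
| 8, 15 | 27.3% | 33.3% | 32.5% | 45.5% |
| 8, 15, 18 | 27.3% | 37.5% | 35.7% | 54.5% |
| 36, 38 | 27.3% | 33.3% | 27.3% | 45.5% |

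Kaplan-Meier lies between the two crude readings. It equals the dropped figure when all losses precede the first death, and the all-ITT figure when all losses follow the last. With early losses, dropping is off by 33.3 − 32.5 = 0.8 or 37.5 − 35.7 = 1.8 points, and all-ITT by 32.5 − 27.3 = 5.2 or 35.7 − 27.3 = 8.4. With late losses, dropping is off by 33.3 − 27.3 = 6.1 (unrounded) and all-ITT by nothing. The ceiling with three losses is 3/8 − 3/11 = 10.2 points.

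**Difference between arms (active minus control).** Assume 2/11 active deaths (Days 15, 30) and 3/11 control deaths (Days 10, 20, 30).

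| Losses (Days 5 and 12) | All ITT | Dropped | Kaplan-Meier | Unknown as dead |
|---|---|---|---|---|
| none | −9.1 | −9.1 | −9.1 | −9.1 |
| two, active arm | −9.1 | −5.1 | −5.1 | +9.1 |
| two, control arm | −9.1 | −15.2 | −14.3 | −27.3 |

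**Interval.** Clopper-Pearson gives limits for one proportion, not for a difference. A plain Greenwood interval is not a good replacement. Without censoring it reduces to the Wald interval. Summing the binomial probabilities of all 12 × 12 outcomes at n = 11 and true rates of 19.3% and 27.5%, nominal 95% Wald limits cover 91.8% of the time. The chance that at least one arm has no deaths, where the Greenwood variance is zero, is 1 − (1 − 0.807^11)(1 − 0.725^11) = 1 − (1 − 0.095)(1 − 0.029) = 12%. A score-type limit does not collapse there: for 0/11 its upper end is 3.84/(11 + 3.84) = 25.9%.

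**The case against.** The strongest reply is that the trigger may never occur. Vital status is collected at Days 42 and 84 by visit or telephone (Protocol 11.1.1.6 and 15.23), and stopping treatment is not the same as leaving the study (Protocol 12.3). With complete status there is nothing to resolve. This stands as a limit on size. It does not supply a rule for when contact fails, and both Protocol 12.3 and the censoring in SAP 8.2.2 anticipate withdrawal and loss.

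Second, the only written denominator rule is 13.2.5.2, which points to dropping, and with early losses that is within 2 points of Kaplan-Meier. Fair, but 8.2.3 does not confirm that reading, and with late losses the gap is 6.1 points. The Unknown or Missing category in the same section would disclose the count without settling the rate.

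Third, overall survival and the percentage who died are separate secondary endpoints, and Protocol 19.7.2 plans Kaplan-Meier in addition to the mortality difference. Two displays are therefore intended. But both estimate the probability of death by the same day, so they should agree, and stating a fixed denominator alone would only choose one of the two distortions.

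Fourth, Kaplan-Meier assumes that those lost resemble those who stay, which is doubtful if the sickest withdraw. That stands, and is why a sensitivity table is needed.

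A reader might go further and infer that the mortality comparison will be biased, or that SAP 6.3 orders withdrawn subjects to be counted as alive. The documents support neither: they give no number of unknowns, and 6.3 assigns no vital status.

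**Conclusion.** The gap is real but conditional. SAP 8.2.3 does not say how unknown vital status enters the mortality rates, and its crude rates can depart from the Kaplan-Meier figures in 8.2.2. If no status is unknown and both sections use one time origin, they agree exactly. With two or three unknowns among 11, the per-arm departure runs from nothing or under 2 points to about 8 in the worked cases, with a ceiling of 10.2. These figures rest on assumed losses, dates and three deaths per arm.

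The consequence is for consistency and interpretation, not error rates: the trial is exploratory, safety is primary, DRC-assessed Global Response is the key efficacy evaluation, and enrollment stopped at 22. At 3/11 against 3/11 even a Wald interval is about ±37 points (1.96 × √(2 × 0.273 × 0.727/11) = 0.37), so the choice is unlikely to change a conclusion. I rate it minor to moderate.

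**What to change.** 1. **Correct 8.2.2 first.** Its censoring sentence names subjects who died; it must mean those who did not. Choose one time origin for 8.2.2 and 8.2.3.
2. **Redefine the difference in 8.2.3** as the difference between the 8.2.2 Kaplan-Meier estimates at Day 42 and at Day 84, in the ITT population.
3. **Replace the interval.** Combine per-arm score-type limits into an interval for the difference, using as effective sample size S(1 − S) divided by the Greenwood variance, where S is the Kaplan-Meier survival, and the number at risk at the landmark if an arm has no deaths. Log-log limits could be used instead, but they are undefined at 100% survival and need a stated fallback. Use neither plain Greenwood/Wald limits nor single-proportion Clopper-Pearson.
4. **Report** the number with unknown status per arm at each day, and one sensitivity table counting them as dead. Keep the raw death counts and attribution as description.
5. **Record the choice** in SAP Section 12.

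Cost: SAP wording and a little programming for the interval and one table; no new data. The price is reliance on non-informative censoring, which the sensitivity table checks.
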